12.5.3.2 Vital signs

All vital signs data will be listed by treatment group, participant, and visit/time and if ranges are available, abnormalities (and relevant orthostatic changes) will be flagged. Summary statistics will be provided by treatment and visit/time. Change in SBP/DBP from baseline to day 360.

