2.7.4 Other safety data

2.7.4.1 Vital signs

Notable abnormal vital signs data will be listed by treatment group, participant, and visit/time and if ranges are available, abnormalities will be flagged.

Number and percentages of participants notable vital sign values at screening and newly occurring or worsening notable values any time post-baseline as defined in [Section 5.4](#) will be tabulated.

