Analysis of adverse events will be done for TEAEs. Protocol section 12.5.3 describes that additionally, all summary tables for AEs will be repeated for on-treatment AEs only (TEAEs). This repetition will not be done.

First dose of double-blind treatment (Day 1) will be considered for the analyses, even if protocol mentions time of randomization. Day 1 and randomization date of some participants may not be the same, therefore Day 1 is considered for consistency of the analyses.

There will not be a separate table for exclusions from the analyses set, as there are no PDs defined excluding participants from an analysis set and exclusions are covered by the definition of the analyses set. Therefore, analysis would be redundant with other tables.

Region and country will not be summarized for the randomized set, countries are summarized on the FAS.

Supplementary analyses presenting relative risk and risk difference will be presented using CMH with Mantel-Haenszel estimators for both measures and will not be based on score statistics.

Descriptive summary of all vital signs data will not be provided, number and percentages of participants with notable abnormal vital signs will be provided instead. Listing of vital signs will be limited to the notable abnormal vital signs.

5 Appendix

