5.4 Laboratory parameters derivations

[Table 5-1](#), [5-2](#), [5-3](#) and [5-4](#) show the criteria for clinically notable liver test values, renal function, skeletal muscle function and vital signs, respectively.

When a criterion contains multiple laboratory parameters, the criterion will only be considered to have been met when all conditions occur on the same assessment. A case where all criteria are met at a post-baseline time point will be considered as newly occurring if the criteria are not met at baseline and will be considered as worsening if the criteria are met at baseline and at least one component is worsening from baseline irrespective of whether the other(s) are better.

For additional safety monitoring see Section 10.2.2 and 10.2.3 of Protocol.

Table 5-1 Notable liver function test values

Criterion
ALT $\geq 3 \times$ the upper limit of normal range (ULN)
ALT $\geq 5 \times$ ULN
AST $\geq 3 \times$ ULN
AST $\geq 5 \times$ ULN
ALT or AST $\geq 3 \times$ ULN
ALT or AST $\geq 5 \times$ ULN
Total bilirubin $\geq 2 \times$ ULN
ALP $\geq 2 \times$ ULN
ALT or AST $\geq 3 \times$ ULN and total bilirubin $\geq 2 \times$ ULN
ALT = alanine aminotransferase, AST = aspartate aminotransferase, ALP = alkaline phosphatase

Table 5-2 Notable renal function

Criterion
eGFR ≥ 30 and ≤ 60 ml/min /1.73m ²
Moderate renal impairment
eGFR < 30 ml/min/1.73m ²
Severe renal impairment
eGFR = Estimated glomerular filtration rate

Table 5-3 Notable skeletal muscle values

Criterion
CK $> 5 \times$ the upper limit of normal range (ULN)
CK = Creatine kinase

Table 5-4 Notable Criteria for Vital Signs

Vital sign	Notable abnormalities
Pulse (bpm)	<40 or >180
BP (mmHg)	Systolic (SBP)
	<40 or >180 for Screening Visit
	<40 or >220 for Other Visits
	Diastolic (DBP)
	<40 or >110 for Screening Visit
	<30 or >130 for Other Visits

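### The SAP drops the protocol's post-baseline vital-sign summaries, and the extreme-value counts that replace them would be nearly empty

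*SAP*

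**What the plan says.** Protocol 12.5.3.2 sets out three things for vital signs: a full listing ("All vital signs data will be listed by treatment group, participant, and visit/time"), and then "Summary statistics will be provided by treatment and visit/time. Change in SBP/DBP from baseline to day 360".

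SAP section 4, which lists departures from the protocol, states: "Descriptive summary of all vital signs data will not be provided, number and percentages of participants with notable abnormal vital signs will be provided instead". It also cuts the listing to notable values. No reason is given, although the same section explains some of its other changes, such as using Day 1 in place of the randomization date.

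SAP 2.7.4.1 keeps a tabulation of notable values at screening and of "newly occurring or worsening notable values any time post-baseline". Table 5-4 in SAP 5.4 defines notable:

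| | Screening | Other visits |
|---|---|---|
| SBP (mmHg) | "<40 or >180 for Screening Visit" | "<40 or >220 for Other Visits" |
| DBP (mmHg) | below 40 or above 110 | below 30 or above 130 |
| Pulse (bpm) | below 40 or above 180 | same |

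The protocol is no source for these limits: its Appendix 16.1, on clinically notable laboratory values and vital signs, is marked not applicable.

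**The concern.** A count of values beyond very wide limits does not do the work of a summary by arm and visit. It says nothing about a shift in the mean, and it ignores any individual change that stops short of the limit. Laboratory data keep shift tables by visit (SAP 2.7.3), whereas vital signs keep nothing comparable after baseline.

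Blood pressure is relevant in this population. Protocol 5.1 lists a pressure of at least 180/110 mmHg among the high-risk entry criteria, and Protocol 3.4 asks that high blood pressure be optimally treated during the double-blind period. Vital signs are collected throughout the treatment period. At stake is whether the study report contains any usable between-arm description of those data.

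**Working it through.** The documents give no figure to reproduce here, so the check has two parts: what the reporting rules count, and how full the resulting table would be.

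**Rules alone.** After screening, SBP counts only below 40 or above 220. A participant who goes from 150 to 219 mmHg is never tabulated or listed, whatever distribution is assumed. The same holds for any DBP rise that stays at or below 130.

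**Number of readings.** Protocol Table 8-1 schedules vital signs after baseline on Days 30, 90, 150, 210, 270, 330 and 360, which is seven visits. SAP Table 2-1 has an analysis window for each. With the planned 1760 participants and complete attendance, 1760 × 7 = 12,320 readings, or 6,160 per arm. Each blood-pressure value is the mean of three measurements (Protocol Table 8-2).

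**Assumptions (not in the documents).** SBP is roughly normal with mean 130-140 and SD 15-20 mmHg. DBP is roughly normal with mean 80-85 and SD 10-12 mmHg.

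**Expected readings outside the limits** = number of readings × normal tail area.

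- SBP above 220, mean 130, SD 15: z = (220 − 130)/15 = 6, tail 9.87 × 10⁻¹⁰; × 12,320 = 0.00001.
- SBP above 220, mean 140, SD 20: z = 4, tail 3.17 × 10⁻⁵; × 12,320 = 0.39.
- SBP below 40, worst case mean 130, SD 20: z = −4.5, tail 3.40 × 10⁻⁶; × 12,320 = 0.04.
- DBP above 130, mean 80, SD 10: 0.0018 per arm. Mean 85, SD 12: 0.54 per arm, or about 1.1 in the trial.

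**If one arm rose uniformly by 10 mmHg in SBP.** The expected number above 220 in that arm is still at most 1.4 (mean 150, SD 20: tail 2.33 × 10⁻⁴ × 6,160). A comparison of the counts above 220 would have power of about 0.05 (mean 135, SD 18) to 0.16 (mean 140, SD 20). With counts this close to zero, these powers are only approximate.

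**How far the tail assumption would have to be wrong.** For even 10 readings above 220, the tail area would have to be 10/12,320 = 8.1 × 10⁻⁴, about 26 times the largest value assumed above.

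**What the dropped summary would give.** The 95% half-width for the arm difference in mean SBP change is 1.96 × SD × √(2/880), where SD is that of the change.

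- SD 15: 1.40 mmHg.
- SD 20: 1.87 mmHg.
- If the SD at a single visit is 20 and the baseline-to-Day 360 correlation is only 0.3, the SD of change is 20 × √(2 × 0.7) = 23.7 and the half-width is 2.2 mmHg.

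These assume complete Day 360 data on 880 per arm. With an SD of change of 15-20, the two-sided 5% power is 0.88-0.99 for a 3 mmHg difference and above 0.99 for 5 mmHg. The protocol plans no test here; the figures only show how much information the data hold.

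**The case against.** The strongest reply is that this is an openly declared change, made before database lock, to a parameter that is neither a primary nor a secondary endpoint, for a drug whose safety profile the protocol calls well characterized. That is true, and it limits the weight of the point. It does not supply the missing reason or make the replacement informative.

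Several stronger readings are tempting and should not be drawn.

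- *The trial would report essentially no blood-pressure safety data.* Not so. Baseline SBP, DBP and pulse are summarized by arm (SAP 2.3.2). Treatment-emergent events are tabulated by system organ class, preferred term, severity and SMQ (SAP 2.7.1), and Protocol 10.1.1 makes clinically significant abnormal results reportable as adverse events. Hypertension or hypotension reported in this way would appear. That route depends on investigator judgement and gives no between-arm estimate of blood pressure.
- *No between-arm blood-pressure result exists anywhere.* The documents cannot show this. Section 4 does not name the Day 360 change explicitly, SAP 5.5.2.4 specifies an ANCOVA for unnamed traits, and several exploratory sections are redacted. Only the visible plan can be judged.
- *The wider limits after screening make the count of worsening compare unlike with unlike.* They normally do not. SAP 5.4 judges new or worsening values against baseline, and SAP 2.1.1.5 defines baseline as the last value before the first injection. That is normally Day 1, which falls under the same limits as later visits. A participant at 185 at screening and 215 on treatment is therefore not a failed worsening comparison. A mismatch arises only if Day 1 values are missing and a screening value serves as baseline.
- *All limits loosen after screening.* Only the SBP upper limit and both DBP limits widen. The SBP lower limit and the pulse limits are unchanged.
- *The SBP lower limit of 40 is an error.* It coincides with the screening DBP limit and invites a check, but no passage gives another value.

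The reply can also fairly say that normal tails at four to six SDs are not to be read literally, especially when entry at or above 180/110 is possible. The small figures show order of magnitude only.

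**Conclusion.** The point holds for the visible plan. SAP section 4 withdraws the protocol's post-baseline descriptive summaries without a stated reason, and "Change in SBP/DBP from baseline to day 360" has no visible counterpart in the SAP. What remains, besides baseline summaries and adverse events, is a table that on the assumed distributions would hold well under one SBP reading above 220 and at most about one DBP reading above 130 among some 12,320. It could not show a between-arm shift, or an individual rise that stays below 220/130 mmHg.

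The sizes rest on assumed means and SDs and on normality, but the conclusion does not depend on where in the range one stands, and the 150-to-219 case follows from the rule alone. This is a gap in safety reporting. It does not touch the primary or secondary results, and it does not mean that worsening blood pressure would go unreported as an adverse event.

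**What to change.** Delete the vital-signs change from SAP section 4. Restore the summaries of SBP, DBP and pulse by treatment and visit, with the change in SBP and DBP from baseline to Day 360 as in Protocol 12.5.3.2, using the vital-sign windows already in SAP Table 2-1. If the sponsor prefers to keep the change, section 4 should give the reason.

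Separately, check and justify the reporting limits in Table 5-4, including the SBP lower limit of 40 and the different upper limits at screening and afterwards. These are reporting limits, and no particular values are proposed here.

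The cost is one additional standard safety table and a short review of Table 5-4. No new data are needed.

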5.5 Statistical models

5.5.1 Analysis supporting primary objective(s)

5.5.1.1 (Binary) Logistic regression

The primary endpoint will be analyzed using a binary logistic regression of the following form:

$$\text{logit}(LDL \leq LDL \text{ target}) = \text{treatment} + CV \text{ risk category}.$$

In SAS the PROC LOGISTIC procedure will be therefore used. The ODDSRATIO statement will be used to estimate the odds ratio. The E option will be used to obtain a table of coefficients of the linear combination of parameters that define the log odds for each treatment group. Odds

ratios will be presented with associated two-sided 95% confidence interval for treatment comparison.

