4.6 Rationale for Public Health Emergency mitigation procedures

During a public health emergency as declared by local or regional authorities e.g.. pandemic, epidemic or natural disaster, mitigation procedures to ensure participant safety and trial integrity may be implemented. Notification of the Public health emergency as declared by local or regional authorities should be discussed among investigators and Novartis. All procedures adapted to the situation must be submitted, if required as per local regulations, through a protocol amendment for approval by Local or Regional Health Authorities and Ethics Committees prior to implementation of mitigation procedures.

5 Study Population

The study population consists of adult participants at very high and high risk for cardiovascular events as defined by the cardiovascular risk categories in the 2019 ESC/EAS guidelines for the management of dyslipidemias ([Mach et al 2020](#)) who do not meet their individual LDL-C target despite being treated with their individual MTD of a statin for at least 30 days, and if applicable, another LLT on top of statin stable for at least 30 days prior to screening (up to approximately 20% of randomized participants).

Among the defined study population, treatment with inclisiran on top of an ongoing individually optimized LLT is suggested to be especially beneficial for subpopulations suffering from PAD and CHD with stable angina pectoris (AP). These participants have been shown to respond to

LLT with improved functional capacity and quality of life ([Mohler 2003](#), [Mondillo et al 2003](#), [Kabaklić and Fras 2017](#), [Manfrini et al 2020](#)).

AP or 'chest tightness' describes a thoracic or retrosternal pain that occurs frequently in the form of attacks and is triggered by myocardial ischemia. AP is the cardinal symptom of CHD and can be distinguished into stable and unstable AP periods, categorized as either chronic syndromes (CCS) or acute coronary syndromes (ACS). Stable AP is characterized by chest pain that can be reproduced by physical or psychological stress and that disappears at rest or after administration of nitroglycerine ([Knuuti et al 2020](#)).

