5. Participant on a stable dose of a statin for \geq 30 days. (Please refer to [Table 3-1](#) for statin enrollment targets.). [The investigator must ensure that the participant's individual statin therapy does not meet any contraindication for that participant and does not interfere with the listed eligibility criteria as stated in the local SmPC of the respective statin.].
6. Up to approximately 20% of total participants can be on a stable dose (for \geq 30 days prior to screening) of another LLT on top of statin such as a cholesterol absorbing inhibitor or a bile acid sequestrant, or alternatively, an adenosine triphosphate citrate lyase (ACL) inhibitor, as indicated.
7. Fasting triglyceride < 400 mg/dL.

At Baseline:

8. Fasting triglyceride < 400 mg/dL.
9. Before randomization, despite being treated with the individual MTD of a statin for \geq 30 days and, if applicable, with another LLT on top of statin (stable for \geq 30 days),
 - a. in participants with very high cardiovascular risk: serum LDL-C \geq 55mg/dL.
 - b. in participants with high cardiovascular risk: serum LDL-C \geq 70mg/dL.

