12.4.1 Definition of primary endpoint(s)

The primary endpoint for this study is the proportion of participants achieving their individual LDL-C target (< 55 mg/dL or < 70 mg/dL) at day 90. The participant-individual LDL-C target depends on their cardiovascular risk category as defined in the 2019 ESC/EAS guidelines for the management of dyslipidemia (Mach et al 2020). The individual LDL-C target (< 55 mg/dL or < 70 mg/dL) will be evaluated according to the most recent assessment of the cardiovascular risk category as determined by the investigator. Accordingly, the achievement of the participant-individual LDL-C target forms a binary response variable for LDL-C target. The primary endpoint will be analyzed based on the FAS.

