1.2.1 Primary estimand(s)

The estimand is the precise description of the treatment effect and reflects strategies to address events occurring during trial conduct which could impact the interpretation of the trial results (e.g. premature discontinuation of treatment).

The primary clinical question of interest is: What is the effect of inclisiran versus placebo on top of an ongoing individually optimized LLT on achieving the individual LDL-C target at Day 90 in very high risk and high risk participants as defined in the 2019 ESC/EAS guidelines for the treatment of dyslipidemias ([Mach et al 2020](#)).

The primary estimand is described by the following attributes:

1. **Population:** Adult participants categorized as very high risk or high risk as defined by the CV risk categories in the 2019 ESC/EAS guidelines for the management of dyslipidemias ([Mach et al 2020](#)) with elevated LDL-C despite being treated with the individual MTD of statin and, if applicable, also other LLT. Further details about the population are provided in Section 5 of the protocol
2. **Endpoint:** Proportion of participants achieving individual LDL-C target (< 55 mg/dL or < 70 mg/dL) at Day 90. The individual LDL-C target of the participants is determined according to their individual CV risk category.
3. **Treatment of interest:** Inclisiran, compared to placebo, both on top of an ongoing individually optimized LLT. Randomized treatments are the investigational treatment inclisiran or the placebo control treatment. In both treatment arms, participants receive an individually optimized rosuvastatin therapy for reaching the individual LDL-C target and tolerability. If required to achieve their LDL-C target, further individually optimized LLT can be administered. Additional information about the investigational treatment and control treatment are provided in Section 6 of the protocol.
4. **Summary measure:** The odds ratio of achieving individual LDL-C target at Day 90 compared between treatment arms. A larger proportion of participants indicates a superior outcome.

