2.5.1 Primary endpoint(s)

The primary endpoint for this study is the proportion of participants at Day 90 achieving their individual LDL-C target of less than 55 mg/dL or less than 70 mg/dL, i.e. <55 mg/dL for participants with very high cardiovascular risk and <70 mg/dL for participants with high cardiovascular risk. The participant-individual LDL-C target depends on their cardiovascular risk category at time of the LDL-C measurement and will be evaluated according to the most recent assessment of CV risk as determined by the investigator. Accordingly, the achievement of the participant-individual LDL-C target forms a binary response variable for LDL-C target ("achieved"/"not-achieved") and will be analyzed in the FAS.

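### SAP 5.5.1.1 writes the primary model with LDL-C at or below target, while the endpoint and eligibility rules treat a value exactly at 55 or 70 mg/dL as not at target (minor correction)

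*SAP*

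**What the plan says.** The success rule is given in several places.

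- **SAP 5.5.1.1, model for the primary endpoint:** "LDL \leq LDL \text{ target}) = \text{treatment} + CV \text{ risk category". The sign is ≤, so equality is a success.
- **SAP 2.5.1, in words:** "achieving their individual LDL-C target of less than 55 mg/dL or less than 70 mg/dL".
- **SAP 2.5.1, in symbols:** "<55 mg/dL for participants with very high cardiovascular risk and <70 mg/dL for participants with high cardiovascular risk".
- **SAP 1.2.1, primary estimand:** "Proportion of participants achieving individual LDL-C target (< 55 mg/dL or < 70 mg/dL) at Day 90".
- **Protocol 12.4.1:** "proportion of participants achieving their individual LDL-C target (< 55 mg/dL or < 70 mg/dL) at day 90".

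Eligibility uses the complementary side of the same thresholds. Protocol 5.1, criteria 4 and 9, reads "in participants with very high cardiovascular risk: serum LDL-C" with ≥ 55 mg/dL, and "in participants with high cardiovascular risk: serum LDL-C" with ≥ 70 mg/dL. Protocol Section 5 describes the people so enrolled as those "who do not meet their individual LDL-C target despite being treated with their individual MTD of a statin for at least 30 days".

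SAP 2.5.4 and step 6 of SAP 5.5.3, which turn imputed LDL-C into the binary response, name no operator. SAP Section 4, which lists departures from the protocol's analyses, does not mention this one.

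**The concern.** A primary binary response needs one definition. Here the endpoint text and the model formula disagree about a participant whose Day 90 value equals the target. Under the formula, someone correctly randomized at 55 mg/dL as not at target, and still at 55 on Day 90, would be a responder without any change.

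The formula stands beside the named SAS procedure and carries the only explicit comparison with the target in the SAP's statistical appendix, so a programmer could code from it. The same response also feeds the sensitivity analysis (SAP 2.5.5), the Cochran-Mantel-Haenszel estimates (2.5.6.1), the supplementary PCSK9 analysis (2.5.6.3) and the subgroups (2.2.1), so a coding slip would carry through to them.

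**Working it through.** **Step 1: classify a tie under each rule.**

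| Source | Very high risk, LDL-C = 55 | High risk, LDL-C = 70 |
|---|---|---|
| SAP 2.5.1, SAP 1.2.1, Protocol 12.4.1 (<) | not achieved | not achieved |
| Protocol 5.1, criteria 4 and 9 (≥ qualifies) | eligible, so not at target | eligible, so not at target |
| SAP 5.5.1.1 (≤) | achieved | achieved |

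The first two rows agree and the third contradicts both. For any value other than an exact tie, all three agree.

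**Step 2: how many ties could there be?** The plan has no figure to reproduce: the assumed response rates are blacked out, and reporting precision and the Day 90 mean and SD are not given. What follows is an illustration. Only the targets and the 880 planned per arm come from the documents.

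Assumptions:
- LDL-C is reported in whole mg/dL.
- Day 90 LDL-C is lognormal with mean m and coefficient of variation k.
- Placebo means are 70 to 90 mg/dL, inclisiran means are 40 to 65 mg/dL, and k is 0.35 or 0.50.
- The whole arm has a single target t, either 55 or 70.

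Formulas, with Φ the standard normal distribution function:
- s² = ln(1 + k²); μ = ln(m) − s²/2; F(x) = Φ((ln x − μ)/s)
- success under <: F(t − 0.5); success under ≤: F(t + 0.5); tie proportion: the difference
- odds ratio = [p1/(1 − p1)] / [p0/(1 − p0)], with p1 for inclisiran and p0 for placebo, without adjustment for risk category

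Worked case: t = 55, k = 0.35, inclisiran mean 55, placebo mean 90.
- s² = ln(1.1225) = 0.1156, so s = 0.340.
- Inclisiran: μ = 4.0073 − 0.0578 = 3.9496; F(54.5) = 0.557; F(55.5) = 0.578; ties 2.10%, or 0.0210 × 880 ≈ 18 participants.
- Placebo: F(54.5) = 0.096; F(55.5) = 0.105; ties 0.94%, or 0.0094 × 880 ≈ 8 participants.
- Odds ratio 11.86 under <, 11.64 under ≤ (from unrounded proportions): 11.64/11.86 − 1 ≈ −1.8%.

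Six of the 20 scenarios run, including both extremes of the odds-ratio shift:

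| Target | k | Means, placebo / inclisiran | Ties, inclisiran / placebo | OR under < | OR under ≤ | Shift |
|---|---|---|---|---|---|---|
| 55 | 0.35 | 90 / 55 | 2.10% / 0.94% | 11.86 | 11.64 | −1.8% |
| 55 | 0.35 | 80 / 55 | 2.10% / 1.38% | 6.19 | 6.13 | −1.0% |
| 55 | 0.50 | 75 / 65 | 1.52% / 1.41% | 1.631 | 1.629 | −0.1% |
| 55 | 0.35 | 70 / 40 | 1.16% / 1.84% | 15.36 | 15.52 | +1.1% |
| 70 | 0.50 | 75 / 65 | 1.12% / 1.20% | 1.628 | 1.629 | +0.1% |
| 70 | 0.35 | 70 / 40 | 0.32% / 1.65% | 20.92 | 21.53 | +2.9% |

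Across all 20, ties run from 0.32% to 2.10% of an arm, about 3 to 18 of 880.

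**Step 3: reporting precision.** With one decimal, the interval counted as a tie is 0.1 mg/dL wide instead of 1, so ties fall about tenfold, to roughly 0.03% to 0.21% (0.3 to 1.8 of 880). Values imputed on a continuous scale practically never equal the target unless rounded.

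**Step 4: direction.** Moving from < to ≤ can only leave an arm's observed success rate unchanged or raise it. The odds ratio can move either way, depending on how ties and success rates differ between the arms.

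**The case against.** The best defence is that the endpoint is already defined. SAP 2.5.1 gives the rule in words and in symbols and says that it forms the achieved / not-achieved variable. Section 5.5.1.1 then specifies a model for that endpoint. Section 5.5 uses shorthand elsewhere too: the pain-day formula in 5.5.2.3 omits the log link, which is given only in the text beneath it. Because the plan states the target itself as an inequality, LDL ≤ target may be loose notation for meeting the target. The SAP also refers to a separate programming dataset specification, cited for date imputation, so 5.5.1.1 need not be what programmers work from. Displayed formulas are also open to transcription error: in the copy read here, the odds ratio in SAP 2.5.2 lacks the division signs of Protocol 12.4.2. The ≤ should be checked against the signed SAP.

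Most of this stands and limits the severity. It does not remove the inconsistency. The ≤ is in the stated model for the primary analysis, SAP Section 4 does not explain it, and no rule was found saying which SAP section prevails.

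A reader might infer that the SAP has redefined the primary endpoint, or that a definite number of participants per arm will be misclassified and the result inflated. The documents support neither. Every statement of the endpoint remains strict. Any head count needs whole mg/dL reporting and assumed means and spreads, and a count based on 55 mg/dL alone also ignores high-risk participants, whose target is 70. Whole-number LDL-C cannot be presumed: SAP 2.1.1.10 uses calculated LDL-C in many cases, and SAP 2.3.2 lists the other cholesterol measures and triglycerides in mmol/L.

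**Conclusion.** The inconsistency holds as a minor correction. SAP 5.5.1.1 conflicts with the plan's own endpoint, estimand and eligibility rule for values exactly at 55 or 70 mg/dL, and is most likely an appendix slip. If it were coded literally, the illustration suggests that about 0.3% to 2.1% of an arm would be reclassified with whole mg/dL values, and about a tenth of that with one decimal. The odds ratio would shift by about −1.8% to +2.9%, with no fixed direction. These sizes depend on the lognormal shape, the assumed means and spreads, and a single target per arm; none of these is in the documents. Nothing shows that the primary conclusion would change. The case for correcting it rests on having one pre-specified response rule, not on a large numerical effect.

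**What to change.** In SAP 5.5.1.1, replace the left-hand side with logit P(LDL-C < individual LDL-C target). Before unblinding, confirm that the single derived response variable uses strict < for observed and imputed values, so that every analysis drawing on it inherits the same rule.

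The Cochran-Mantel-Haenszel, supplementary and imputation sections contain no wrong operator and need no change in wording.

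The cost is one sign in the SAP and a short check of the derivation code. If the program already uses <, no result changes. If it uses ≤, observed success rates will stay the same or fall slightly. Settling this before unblinding removes any question of choosing the operator after seeing the data.
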